## **9.3 – Data Safety and Monitoring**

The primary potential source of risks in this study is the social risk of gathering behavioral information about hookah tobacco use. This includes potential embarrassment and fear of disclosure of potentially sensitive information about waterpipe and other tobacco product use and confidentiality concerns. Additionally, the messages that we will test will include text and images that may be unsettling to certain participants. We have plans in place to protect participants with respect to both of these risks.

Because the primary risks associated with this study are participant privacy and confidentiality, data security and privacy of records are of upmost importance. Participants' privacy and confidentiality will be protected in several ways. We have several institutional and procedural safeguards in place to ensure that all study data are treated as secure and confidential. No data collected on assessments for this research will be directly linked to participant identifying information (e.g., names, birthdates). Any paper study records will be stored in a locked file cabinet within locked offices at Georgetown Lombardi and Duke University study sites in order to ensure records are kept secure. This includes study data collected at the participant recruitment and screening stages. Only the site PIs and authorized staff will have access to these hard copy records.

Participant screening, enrollment, and study tracking will be securely maintained and entered in a dedicated study REDCap database. REDCap is a secure data management resource maintained by Georgetown University's Information Services data center. The REDCap application and databases are secured on Georgetown University Information Service's server with firewall, backup, and environmental and user-level controls. Study eligibility screeners, assessments, and online consents will be separately administered using Qualtrics. Qualtrics is a secure survey software platform, the license for which is maintained by Georgetown University's Information Services. Assessment completion will be monitored in Qualtrics and separately recorded in the REDCap tracking database by study personnel as Qualtrics is monitored. All electronic study data files from REDCap and Qualtrics, and electronic recordings of telephone interviews, will be securely stored on a GUMC/LCCC network drive. This network space is encrypted and directories are password-protected at the individual user level to ensure electronic data files are treated as secure and confidential. Only the PI, co-investigators, and fully trained, authorized study personnel will be granted access to the data after appropriate permissions are established. These data security layers ensure electronic study tracking and assessment data are securely maintained with rigorous access restrictions.

Mobile phone text message prompts and participants' responses among those randomized to the untailored and tailored MMS conditions will be sent and received using Mobile Commons, a secure, encrypted online software system available through a subscription. The study will be administered through a research-dedicated Mobile Commons account and short code (a six digit phone number) that will be used to send and receive messages for the study. This service allows for advance programming of scheduled text message assessments using a script to automate delivery and personalized MMS message

tailoring as described in the research plan. To protect participant confidentiality, prompts will not gather participant identifying information directly. Mobile Commons specializes in providing researchers with an IRB and HIPAA compliant service for text message protocols. Details of Mobile Commons's information security protocols are available in a security document on the Mobile Commons website (<https://uplandsoftware.com/mobilecommons/resources/white-paper/hipaa-text-messaging-whitepaper/>). Participant responses are stored confidentially using a dedicated research identifier that our staff will assign. Participant responses and tracking data such as the dates and times when messages were sent and responses were received will be recorded using their identifier into a secure study database. At the conclusion of the study, the database will be downloaded from Mobile Commons and stored on GUMC/LCCC's secure data server and permanently removed from the Mobile Commons system. Similar backups will be periodically downloaded and stored on GUMC/LCCC servers throughout the study.

Finally, participants will be viewing messages about hookah tobacco use, some of which will include text and visual images emphasizing the potential health harms and addictiveness of waterpipe tobacco and may be upsetting. Although we have not experienced such an adverse event in our research to date testing similar messages for behaviors such as cigarette smoking and the occurrence is unlikely, throughout the enrollment and informed consent process and over the course of the study participants will be encouraged to contact Georgetown Lombardi study staff or the study PI [name] if they have any questions or if they experience feelings of discomfort or distress as a result of participation. We will re-emphasize this again in instructions for all study assessments. In the event that a participant contacts the study staff or the PI and reports experiencing distress, they will be referred to the study co-investigator [name] for consultation and follow-up. [name] is a licensed clinical psychologist and will assess participants who may experience elevated stress and refer these participants for additional follow up as needed.

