**Randomized Controlled Trial.** Following the vanguard pilot, we will conduct a randomized controlled trial to compare the aggregate effects of mobile MMS messages conveying the harms and addictiveness of hookah tobacco use and examine differences between standard and individually tailored messaging approaches. Participants will be 420 young adult hookah tobacco users between the ages of 18-30 recruited from two study sites, Georgetown Lombardi and Duke University. Approximately half of total participants will be recruited from each study site. (Duke University will seek IRB review and approval for the site specific study protocol at their institution's IRB.) Our approach draws from studies previously conducted by the Georgetown investigators (protocols #2017-0987, 2014-1031). Participants will be recruited through flyers, advertisements, and online media detailed below. After confirming eligibility and obtaining consent, participants will complete a baseline assessment online. At the conclusion of the baseline assessment all participants will be provided a link to standard-of-care information about the risks of hookah tobacco use: the Centers for Disease Control and Prevention (CDC) 'Fact Sheet – Hookahs Smoking and Tobacco Use.' We will objectively capture participants' visits to this site by directly recording click-throughs to this link presented at the conclusion of the baseline assessment. Within 1 week of completing the baseline assessment, participants will be randomized to 1 of 3 conditions: 1) a control condition receiving no additional message content; 2) an untailored MMS condition; and 3) a tailored MMS condition. The MMS exposure will occur for 6-weeks. Participants randomized to both MMS conditions will receive prompts delivered to their mobile phones by an interactive messaging system on two days each week assessing hookah tobacco perceptions and behavior. After responding, participants will immediately receive MMS messages on harms and addictiveness of hookah tobacco. For the tailored MMS condition, messages will be tailored to baseline measures of hookah beliefs and behavior, and dynamically during the intervention period to responses to the interactive text message exchanges. Those randomized to the control condition will not receive messages after the baseline assessment.

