All participants will complete follow-up assessments online 6-weeks post baseline (Follow-Up 1), 3-months later (Follow-Up 2), and 6-months later (Follow-Up 3). We carefully chose these time points based on our team's preliminary work on hookah tobacco messaging [21], recommendations for follow-up duration in tobacco intervention research [22, 23], and because this follow-up frequency and duration will capture short term message effects and changes in hookah tobacco use and mediating processes over time [5, 13, 21, 22, 24-27].

The specific aims are as follows:

**Aim 1:** Examine the overall effects of theoretically informed messages conveying harms and addictiveness of hookah tobacco on waterpipe tobacco perceptions and behavior.

H1: Mobile MMS messages will increase perceived risk and worry about harms and addictiveness of hookah tobacco and motivation to quit, reduce frequency of hookah use, and increase cessation relative to the control condition.

**Aim 2:** Investigate the added effects of message content tailored to hookah tobacco perceptions and behavior.

H2: Tailored mobile MMS messages will produce greater increases in perceived risk and worry about harms and addictiveness of hookah tobacco and motivation to quit, greater reductions in frequency of hookah use, and higher cessation rates relative to untailored MMS messages and the control condition.

**Aim 3:** Investigate mediating mechanisms and moderators of message effects on motivation to quit and hookah use.

H3a: MMS message effects will be mediated by greater perceived risk and worry about harms and addiction and greater receptivity and emotional responses to the messages.

H3b: MMS message effects will be greater among monthly users versus more frequent users, less dependent users versus more dependent users, and exclusive hookah users versus those who also use other tobacco products.

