### **8.1.1 Randomize Trial Procedures:**

After confirming eligibility and obtaining consent, participants will complete a baseline assessment online. The baseline assessment will be administered using Qualtrics as with online assessments and consent described above. Participants will receive a unique survey link to complete the baseline assessment, sent to them from study staff via email. This link allows us to track completion of the baseline assessment for each participant, and is encrypted to ensure confidentiality and privacy. Participants' completion of the survey will be monitored in Qualtrics and tracked in the study REDCap tracking database by study staff. The baseline survey will consist of validated items assessing participant characteristics (e.g., demographics), hookah tobacco smoking behavior, use of other tobacco products, and comprehensive assessment of hookah tobacco attitudes, beliefs, and perceptions of harms and addictiveness. Details of measures are described below, and an example of the survey is attached.

After completing the study baseline assessment online, participants will be randomized in approximately equal numbers to the three study conditions: 1) a control condition receiving no message content; 2) an untailored MMS condition; and 3) a tailored MMS condition. Randomization will be implemented using an algorithm within the study REDCap database. Randomization and the 6-week message exposure period for the untailored and tailored MMS conditions will begin within one week of completing baseline. Our approach to text message prompt and MMS message delivery is informed by prior research and the unique contexts of young adults' waterpipe tobacco use. At enrollment, we will assess participants' sleep-wake cycles and preferred times of day for message delivery. This will be included as data uploaded to schedule text message prompts and MMS message delivery. We use this strategy in our text messaging studies to maximize protocol adherence and retention [49-52].

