Participants in both MMS conditions will interact with the messaging system by responding to up to two text message prompts delivered to their personal mobile phones on two days each week during the 6-week exposure period (i.e., responding to up to a total of four text message prompts per week). Prompts will be delivered on two days each week based on the timing of participants' enrollment to target the timing and social contexts in which young adults use hookah tobacco [11]. The text message prompts will capture hookah tobacco use and cognitive and emotional aspects of perceived harm and addictiveness based on measures from our recent work [35, 53]. After responding to prompts, participants will immediately receive an untailored or tailored MMS message based on the conditions to which they are randomized. This dose of text message prompts and MMS messages is based on typical patterns of young adult waterpipe tobacco use (i.e., usually non-daily use) and recommendations for message dose in mobile behavior change programs to ensure sufficient exposure and avoid burnout over time [54-56]. Total MMS messages delivered to participants will vary depending on frequency of responses to the text message prompts, which will enable us to explore MMS message dose effects in analyses [55].

MMS messages will be sent and received using the software platform Mobile Commons [57]. Mobile Commons has an extensive track record supporting NIH and privately funded research and provides the technology backbone for the NCI's national SmokeFreeTxt program. Mobile Commons provides researchers with a user-friendly, secure platform to implement interactive mobile phone text and MMS messaging protocols. The platform features a content management system that allows for the creation of preprogrammed, automated schedules to send messages and collect responses without the need for technical programming. Messaging protocols are implemented as branching tree structures specifying the parameters for delivery of text message prompts, collection of participant responses, and triggers for message content delivered in return.

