#### **8.1.4. Measures**

The proposed measures for this study have all been validated and found to be reliable assessments across our studies and research by others. These measures follow recommendations for assessment of hookah tobacco use and related constructs. Baseline measures will assess demographics, motivation to quit hookah tobacco (9,10) and frequency of use in the past 30 days (9, 140) as the primary outcomes, as well as hypothesized mediators (9,10), moderators (9,10, 28,37), and potential covariates (4-6,21,28, 80,87,143,144-149). Follow-ups at 6-weeks (Follow-Up 1), 3-months (Follow-Up 2), and 6-months (Follow-Up 3) will measure similar outcomes. For details of measures to be implemented at each of these time points please see the attachments in Section 12.9.

**8.1.5 Study Retention & Follow-Up Procedures:** Assessment completion will be monitored in real time through Qualtrics and tracked in the study REDCap database by the Georgetown Lombardi study staff. The RA will conduct telephone/email follow-up with participants to ensure assessments are completed according to the protocol and to address any questions or challenges encountered. Participants will also be encouraged to contact research staff if they encounter any difficulties with study procedures. For the MMS conditions, message delivery and receipt will be recorded in real time in Mobile Commons and the RA will follow up by phone with participants as needed to provide technical support, resolve any problems, and bolster adherence. Participants will receive gift cards to acknowledge their time devoted to achieving study milestones: \$20 for baseline, \$25 for the 6-week and 3-month follow-up, and \$30 for completing the 6-month follow-up. Vanguard pilot participants will receive an additional \$10 gift card for each telephone interview completed. We have used these procedures in our research described above with good adherence to online and mobile messaging protocols and high prospective sample retention (Protocol 2014-1031).

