## 4 DSMB – No

## 5 Safety monitoring

Safety monitoring will be performed by the Principal Investigator [name] and in consultation with study co-investigators as needed. Participants will receive full contact information to the study investigators and the IRB as part of the informed consent process to report any issues or adverse events that occur, and will be encouraged to do so in the informed consent process and instructions for online assessments.

For all components of this research, safety data will be gathered and reviewed by the PI [name]. [name] will be the primary person responsible for evaluating any unanticipated problems and determining whether they affect the risk/benefit ratio of the study and whether modifications to the protocol and consent processes are required. A monitoring report will be generated at the end of each year of the study period. [name] will be responsible for reporting any unexpected problematic events involving any aspect of the study to the local IRB per institutional guidelines. Unanticipated problems to be assessed include adverse events, deviations from the study design or protocol, problems with informed consent, and confidentiality violations. [name] will report unanticipated problems to the IRB within 7 business days of their occurrence, per institutional policy.

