#### 7 Plans for ensuring compliance

[name] will be responsible for reporting unexpected adverse events involving any aspect of the study to the Georgetown IRB according to institutional guidelines. [name] will report unanticipated problems to the IRB within 7 business days of the occurrence. The Georgetown IRB will review such cases and determine what actions must be taken to address or resolve the situation.

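### Upset from the messages is a named risk but, as described, is captured only when a participant contacts staff; one identical survey item in all three arms would be a cheap improvement

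*Protocol*

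**What the plan says.** **The risk.** Protocol section 9.3 gives two sources of risk: disclosure of sensitive information, and messages whose text and images could upset some participants. It states that plans cover both. The section headed 3 Risk/benefits repeats the second risk.

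**How distress is found.** Under 9.3, referral to a co-investigator who is a clinical psychologist begins when a participant gets in touch and reports distress. Participants are encouraged to make contact during enrollment and consent and as the study goes on. The protocol adds: "We will re-emphasize this again in instructions for all study assessments". Section 5 Safety monitoring says participants "will be encouraged to do so in the informed consent process and instructions for online assessments". Section 2 Adverse event says they may make contact whenever they wish.

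**Staff contact.** Section 8.1.5 has the research assistant phone or email participants in general about completing assessments and about difficulties they meet. For the MMS conditions it adds that "the RA will follow up by phone with participants as needed to provide technical support". Under 8.1.2 Study Conditions, controls complete assessments only.

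**Schedule.** Section 2 – Study Design says "The MMS exposure will occur for 6-weeks". Section 8.1.1 says "Randomization and the 6-week message exposure period for the untailored and tailored MMS conditions will begin within one week of completing baseline". Assessments are at baseline, 6 weeks, 3 months and 6 months.

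**Emotional content that is measured.** Section 8.1.1 says "The text message prompts will capture hookah tobacco use and cognitive and emotional aspects of perceived harm and addictiveness". H1 expects worry to rise, and H3a treats emotional response to the messages as a mediator.

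**Reporting.** Section 7 says the responsible investigator "will be responsible for reporting unexpected adverse events involving any aspect of the study to the Georgetown IRB". Section 5 has the PI gather and review safety data and produce a yearly monitoring report. The SAP text covers risk appraisals, motivation to quit, frequency of use and cessation. It contains no summary of harm.

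**The concern.** When a harm is recorded only if participants raise it, the count depends on how often and when they are reminded that they may do so. Here the harm, if it occurs, arises during a 6-week message stream, and no reminder with a stated time falls in the middle of that stream. A participant who is upset in week 2 and stops replying may never appear in the safety record.

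What is at stake is how a low count can be read. The protocol's rationale looks toward population-based use of such messages. A report of no distress would be part of that case, and under the described procedure it could not separate messages that caused no distress from participants who were never asked.

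**Working it through.** The documents give no rate, precision target or analysis for distress, so there is no figure of theirs to reproduce. Three checks apply.

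**1. Where the placed reminders fall**

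Inputs:
- Exposure lasts 6 weeks (section 2 – Study Design).
- Exposure starts *s* weeks after baseline, with *s* between 0 and 1 (section 8.1.1).
- Up to two prompts are sent on each of two days per week (section 8.1.1), so the maximum is 2 × 2 × 6 = 24 prompts over 12 message days.

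Share of exposure elapsed at week *t* = (*t* − *s*)/6, limited to the range 0 to 1.

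| Reminder | Share elapsed | Prompts sent, of up to 24 |
|---|---|---|
| Enrollment, consent, baseline | 0% | 0 |
| Follow-Up 1, week 6, *s* = 1 | (6 − 1)/6 = 83% | 20 |
| Follow-Up 1, week 6, *s* = 0 | (6 − 0)/6 = 100% | 24 |
| Follow-Ups 2 and 3 | 100% | 24 |

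The last row holds whether the 3-month and 6-month visits are counted from baseline or from Follow-Up 1. A survey completed late moves the 83% upward. The continuing encouragement in 9.3 and in section 2 Adverse event has no stated time, channel or frequency during exposure, so it cannot be placed in the table.

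**2. What zero reports would show**

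With 420 randomized in approximately equal numbers, the two MMS arms hold about 420 × 2/3 = 280 participants. For zero reports, the exact one-sided 95% upper bound on the rate of *reported* distress is 1 − 0.05^(1/280) = 0.0106, or 1.1%.

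The reported rate is the true rate multiplied by the fraction of events that reach staff. The 1.1% therefore bounds the true rate only if every event is reported. The documents give no such fraction, so they give no bound on the true rate.

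**3. Whether detection is the same across arms**

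- Reminders in assessment instructions: the same in all three arms.
- Research-assistant follow-up about assessments: the same in all three arms.
- Research-assistant calls about messaging: both MMS arms, not control.
- Prompt schedule and messaging support: the same in the untailored and tailored arms.

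The one difference lies between MMS and control. It would tend to raise detection in the MMS arms. Nothing here separates tailored from untailored.

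**The case against.** The other side has real weight. The study is classed as minimal risk and involves no drug, device or procedure. Section 9.3 calls such distress unlikely and reports none in the team's previous work with similar messages. Encouragement to make contact is stated as continuing. A reminder at the end of exposure still allows someone to report looking back, so late does not mean lost. The vanguard pilot interviews up to 20 recipients of tailored messages at 3 and 6 weeks about content, before the trial starts. The four draft surveys are attachments that are not shown and may already hold a suitable item. All of this stands, and it is why the point is an improvement and not a fault that undermines the trial. It does not supply a described means of asking trial participants about distress. The pilot seeks feedback on messages, not adverse events, and its data stay out of the trial analysis.

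Several stronger readings are tempting, and the documents do not support them:

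- *Harm will certainly be under-counted, by a stated amount.* Assuming that 50% to 10% of events are volunteered would turn the 1.1% into 2.1% to 10.6%. That range comes wholly from the assumed fraction.
- *Reminder timing makes the arms non-comparable.* The timing is identical in every arm. Only the messaging-support calls differ. The documents also promise no comparison of harm by arm.
- *Distress can be found only if volunteered.* Support calls or prompt replies might reveal it, although neither is described as collecting adverse events. Each prompt also precedes the message it triggers.
- *Expected upset would never be counted, because IRB reporting refers to unexpected events.* Section 9.3 itself treats such distress as an adverse event, and section 5 has the PI gather and review safety data. The IRB wording is not the recording rule. What remains is that no text requires a distress contact to be recorded with arm and date.

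**Conclusion.** The point holds as a cheap improvement. As the safety sections describe it, distress from the messages is captured when a participant makes contact. The placed reminders fall at 0% of exposure and then at 83% to 100%, after 20 to 24 of up to 24 prompts. Capture is likely to be incomplete, and few or no reports would not show that the messages are well tolerated. The size of any shortfall is unknown.

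Spontaneous reports may also be detected unequally between the MMS arms and control, but there is no reason in the documents to expect this between the two MMS arms.

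The conclusion rests on the schedule as written, on reading the continuing encouragement as having no fixed time or channel, and on the survey attachments not already containing a distress item.

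**What to change.** 1. Check the draft follow-up surveys. If none has such an item, add one identical question to Follow-Ups 1, 2 and 3 in all three arms, asking whether taking part in the study caused upset or distress. Keep it apart from the worry and emotional-response scales. H1 and H3a expect those to rise, so a higher score there counts as a message effect and cannot serve as a harm signal. The control answers give the background level. Follow-Up 2 covers the up to 24 − 20 = 4 prompts that may still be due at week 6.
2. Record every positive answer and every spontaneous distress contact, expected or not, with arm and date. Route them through the referral that section 9.3 already states.
3. Tabulate both sources by arm, separately, in the yearly monitoring report and in the results. Comparison across arms should lean on the solicited item, because it is asked in the same way of everyone.

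The cost is one survey item, a simple log, a minor IRB amendment and possibly a few more referrals to the co-investigator already named. The item will still miss people who stop completing surveys (section 18 plans on 80% retention at 6 months), so the number answering should be shown beside each count.

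A weekly reminder in the MMS stream is not advised. It would prompt only two of the three arms, and it would add a cue about upset to an intervention meant to work through worry and emotional response.
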